6 SUBJECT SELECTION

6.1 Study Population

The Sol Silverman Oral Medicine Clinic is a major referral center for oral medicine patients including patients with Oral Inflammatory Ulcerative Diseases. Clinical diagnosis of Oral Inflammatory Ulcerative Diseases will be made by the patient's oral medicine specialist. Patients with a confirmed clinical diagnosis of Oral Inflammatory Ulcerative Diseases and with oral symptoms (defined as the worst VAS sensitivity score ≥ 7 over the last week) will be eligible **for participation in this study**. Potentially eligible subjects will be screened by one of the investigators by asking patients to rate their worst oral pain score (0-10) over the previous week. Those answering with at least a score of "7" (1/10) and that meet all other eligibility requirements (see below) will be eligible for enrollment. All patients (and/or parents/guardians) will sign informed consent for participation. All patients will be offered the opportunity to take home the consent form, and call back if they wish to participate.

6.2 Inclusion Criteria

1. Male or female ≥ 18 years of age at Visit 1.

2. Patients with symptomatic (worst VAS sensitivity score ≥ 7 over the last week) Oral Inflammatory Ulcerative Diseases
3. Written informed consent (and assent when applicable) obtained from subject or subject's legal representative and ability for subject to comply with the requirements of the study.

6.3 Exclusion Criteria

1. Patients already on topical or systemic steroids.
2. Inability to comply with study instructions.
3. Uncontrolled intercurrent illness or psychiatric illness/social situations that would limit compliance with study requirements.
4. VAS sensitivity score < 7 .
5. Pregnant women. A urine pregnancy test will be performed for women of child bearing potential.
6. Allergy to fluconazole
7. Allergy to dexamethasone or other steroids
8. Patients on medications that have a strong interaction with fluconazole
9. Patients with advanced liver disease
10. Presence of a condition or abnormality that in the opinion of the Investigator would compromise the safety of the patient or the quality of the data.

7 CONCURRENT MEDICATIONS

There will be no restrictions on concomitant medications or supportive care measures.

All subjects will be treated with fluconazole 200 mg tablets once-a-week dosing for prophylaxis as topical steroid therapy may increase the risk of candidiasis. This is typically very effective at preventing candidiasis in susceptible patients, and since there are no interim clinical visits, this will minimize the risk of secondary infection, which if not detected early, could confound the results at the week 4 evaluation. A single weekly dose of fluconazole is not sufficient to have an impact on therapeutic levels of other medications. Fluconazole is a pregnancy category D drug. As such, pregnant women will be excluded from this study.

Any subjects that are already taking a systemic antifungal medication at the time of study enrollment will continue their prescribed medication and will not need to take the additional weekly fluconazole dose.

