PRIMARY OBJECTIVE	The primary objective of this study is to determine the clinical efficacy and tolerability of compound dexamethasone at 0.5 mg/5 mL in Mucolox™ for the treatment of Oral Inflammatory Ulcerative Diseases as measured by a reduction in oral symptoms between patients treated with compounded dexamethasone 0.5mg/5ml solution in Mucolox™ (group A) and patients treated with topical commercial dexamethasone 0.5mg/5ml solution only (group B).
SECONDARY OBJECTIVES	The secondary objectives are: 
 • To determine the clinical improvement in clinician-reported outcome measures achieved by treatment with topical compounded dexamethasone at 0.5 mg/5 mL in Mucolox™ compared to commercial dexamethasone 0.5mg/5ml solution alone. • To assess the tolerability of Oral Inflammatory Ulcerative Diseases as measured with the 14-item Oral Health Impact Profile (OHIP-14).
NUMBER OF SUBJECTS	30
SUBJECT SELECTION	Inclusion Criteria:

CRITERIA
	
Age 18 years and older.
 
Patients with symptomatic biopsy proven Oral Inflammatory Ulcerative Diseases (worst VAS sensitivity score ≥ 7 over the last week).
 
Ability to understand and the willingness to sign a written informed consent document.
 
Exclusion Criteria: Patients already on topical or systemic steroids.
 
Inability to comply with study instructions.
 
Uncontrolled intercurrent illness or psychiatric illness/social situations that would limit compliance with study requirements.
 
VAS sensitivity score < 7.
 
Pregnant women. A urine pregnancy test will be performed for women of child bearing potential.
 
Allergy to fluconazole
 
Patients on medications that have a strong interaction with fluconazole
 
Patients with advanced liver disease

TEST PRODUCT, DOSE, AND ROUTE OF ADMINISTRATION
	
Dexamethasone 0.5 mg/5mL in Mucolox compounded oral solution swish and spit TID for 4 weeks

CONTROL PRODUCT, DOSE AND ROUTE OF ADMINISTRATION
	
Dexamethasone 0.5 mg/5mL (NDC 00054-3177-63; Roxane Laboratories, Columbus, OH 43216-6532) oral solution swish and spit TID for 4 weeks

DURATION OF SUBJECT PARTICIPATION AND DURATION OF STUDY
	
Subjects will be on study for up to 28 days
 
Screening: day 0
 
Treatment: 28 days
 
Follow-up: Day 28 \pm 5 days
 
The total duration of the study is expected to be 4 weeks.

CONCOMITANT MEDICATIONS	Allowed: all Prohibited: none

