2.1 Risk / Benefit Assessment

2.1.1 Drug side effects and toxicities

Potential side effects with dexamethasone 0.5mg/5mL solution used as an oral topical rinse include an increased risk of developing oropharyngeal candidiasis and systemic absorption. All patients will be prescribed antifungal prophylaxis while on study with fluconazole 200 mg once a week. All participants will be informed that they may withdraw from the study at any time. As a topically applied agent, dexamethasone therapy can be discontinued at any time without any complications. Any noted clinical response will be expected to be reversed in such situations.

Prolonged application of potent topical corticosteroids (e.g., > 50 g of clobetasol propionate or > 500 g of hydrocortisone per week) may lead to short-term hypothalamic-pituitary-adrenal axis alteration. In our study, in case of any systemic absorption, the maximum dose would be 10.5 mg/week (5 mL x 0.1 mg/mL = 0.5 mg/rinse, 3 times/day = 1.5 mg, 7 days/week = 10.5 g). We do not expect there to be significant systemic absorption, and therefore do not expect systemic side

effects of dexamethasone solution when used as a swish and spit. Mucolox™ is a vehicle for drug delivery used in compounding medications with ingredients expected to be harmless. No major side effects from dexamethasone 0.5mg/5mL solution and dexamethasone 0.5mg/5mL solution in Mucolox™ use were reported in our first preliminary study³¹.

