11 DISCONTINUATION AND REPLACEMENT OF SUBJECTS

11.1 Early Discontinuation of Study Drug

A subject may be discontinued from study treatment at any time if the subject, the investigator, or the Sponsor feels that it is not in the subject's best interest to continue. The following is a list of possible reasons for study treatment discontinuation:

- Subject withdrawal of consent (or assent)
- Subject is not compliant with study procedures
- Adverse event that in the opinion of the investigator would be in the best interest of the subject to discontinue study treatment
- Protocol violation requiring discontinuation of study treatment
- Lost to follow-up
- Sponsor request for early termination of study
- Positive pregnancy test (females)

If a subject is withdrawn from treatment due to an adverse event, the subject will be followed and treated by the Investigator until the abnormal parameter or symptom has resolved or stabilized.

All subjects who discontinue study treatment should come in for an early discontinuation visit as soon as possible and then should be encouraged to complete all remaining scheduled visits and procedures.

All subjects are free to withdraw from participation at any time, for any reason, specified or unspecified, and without prejudice.

Reasonable attempts will be made by the investigator to provide a reason for subject withdrawals. The reason for the subject's withdrawal from the study will be specified in the subject's source documents (see below for early termination procedures).

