Appendix 1**INSTRUCTIONS FOR PREPARING & USING YOUR
TOPICAL SOLUTION****WHAT YOU WILL RECEIVE**

- One 480 mL bottle of concentrated solution (5 mg/5 mL)
- 4 tablets of fluconazole 200 mg

USING YOUR SOLUTION

You will be rinsing with your solution **3 times per day**.

1. Gently shake the bottle of solution.
2. Pour 5 mL of solution into the dosing cups provided.
3. Swish the solution in your mouth for 5 minutes, then spit – DO NOT SWALLOW!
4. Do not eat or drink for 15 minutes after rinsing.

Please take one table of fluconazole once a week

CONFIDENTIAL

This document is confidential. Do not disclose or use except as authorized.

	11													
	12													
	13													
	14													

	3													
	15													
	16													
	17													
	18													
	19													
	20													
	21													
	22													
	4													

CONFIDENTIAL

This document is confidential. Do not disclose or use except as authorized.

	23																						
	24																						
	25																						
	26																						
	27																						
	28																						

CONFIDENTIAL

This document is confidential. Do not disclose or use except as authorized.

Appendix 3

DEXAMETHASONE RINSE IN MUCOLOX™ FOR THE TREATMENT OF ORAL INFLAMMATORY ULCERATIVE DISEASES

VISIT #1

Subject Name _____

[figure not shown]
[figure not shown]
Medical Record Number _____

Date of Visit _____

SUBJECTIVE DATA (Over last two weeks unless specified)

MUCOSAL PATHOLOGY

- 1. Does your mouth hurt now? Y/N
- 2. Does it hurt to swallow food or drink? Y/N
- 3. How would you rate your worst mouth sensitivity over the last week?

No sensitivity

Worst sensitivity

CONFIDENTIAL

This document is confidential. Do not disclose or use except as authorized.

[figure not shown]
[figure not shown]
4. Do you avoid any foods because they make your mouth hurt?

- 0 = Not at all
- 1 = Slightly
- 2 = Moderately
- 3 = Quite a bit
- 4 = Extremely

If “yes”, what types of foods?

- a. Spicy foods
- b. Acidic foods
- c. Salty foods
- d. Hard/crunchy/crusty foods
- e. Other:

5. Do you feel that your oral intake (what you eat) is limited by your oral condition? Y/N

Not limited at all

Severely limited

Score: _____

If “Yes”, how limited do you feel it is?

- a. Partial limitation
- b. Severe limitation

6. Have you been bothered by ulcers in the mouth?

- 0 = Not at all
- 1 = Slightly
- 2 = Moderately
- 3 = Quite a bit
- 4 = Extremely

CONFIDENTIAL

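### Drugs that interact strongly with fluconazole are barred at entry but may be started during the trial's own weekly fluconazole (low priority)

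*Combined protocol and SAP*

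**What the plan says.** **At entry.** Exclusion 8 in Section 6.3 reads "Patients on medications that have a strong interaction with fluconazole". The synopsis carries the same criterion.

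**After entry.** Section 7 opens with "There will be no restrictions on concomitant medications or supportive care measures". The synopsis entry on concomitant medications is "Allowed: all Prohibited: none".

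**The trial's fluconazole.** Section 2.1.1 states "All patients will be prescribed antifungal prophylaxis while on study with fluconazole 200 mg once a week". Section 7 makes one exception: a subject already on a systemic antifungal stays on it and skips the trial's weekly tablet. Section 9.2 repeats the exception. Appendix 1 lists 4 tablets of 200 mg and tells the subject "Please take one table of fluconazole once a week". As shown, it says nothing about new drugs.

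**The stated reassurance.** Section 7 adds "A single weekly dose of fluconazole is not sufficient to have an impact on therapeutic levels of other medications".

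**Visits and recording.** Section 9.2 has two visits, baseline and day 28 ± 5 days, and Section 7 itself notes that there are none between. Section 9.1.1 records concomitant drugs at baseline/screening, at Visit 1 and at early termination. It does not name Visit 2.

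**The concern.** The criterion and the on-study rule address the same combination of drugs and give opposite answers. Exclusion 8 treats that combination as a reason not to enrol. Once the subject is enrolled and has been given fluconazole by the trial, the rule that a clinician would look up says that nothing is restricted. This is an explicit permission, so it is more than a missing detail.

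What is at stake is the safety of individual subjects. The fluconazole is given because the protocol requires it, so the protocol should say what to do when another prescriber wants to add a drug that does not go with it.

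**Working it through.** No arithmetic decides this point. It is a comparison of texts.

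1. **Does the entry bar extend past entry?** Exclusion 8 is worded for patients already on such drugs. No section carries it into the treatment period, and none says to withhold fluconazole if such a drug is started.

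2. **Does another on-study rule cover the gap?**
   - Section 9.2 bars other agents only when they are given to treat the oral disease. A drug started for another reason falls outside it.
   - Section 12 counts the use of a prohibited concomitant medication as a violation, but the synopsis prohibits none and no list is given.
   - Section 5.3 asks subjects to report unexpected or lasting side effects. That acts only after a problem has appeared.
   - Section 11.1 lets the investigator stop study treatment in the subject's interest. It permits action but does not call for it.

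3. **Are new drugs on study foreseen?** Yes. Sections 9.2 and 12 expect that some subjects will add immunomodulatory drugs, systemic or topical. Section 12 allows this and makes those subjects unevaluable for the primary endpoint. Neither section asks for a check against fluconazole. The documents do not say whether any such drug interacts, and none is assumed to.

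4. **Does Section 7's sentence on drug levels resolve the conflict?** There are two cases. If the sentence holds for every drug, exclusion 8 turns patients away without need. If exclusion 8 is needed, the sentence is too broad. Either way one text should change. The documents do not show which is right.

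5. **Would a new drug be noticed?** There is no interim visit. Appendices 3 and 4 and the schedule in Section 9.2 make Visit 1 the baseline visit and Visit 2 the end of study. As Section 9.1.1 is worded, a subject who completes the trial has no named point at which a newly started drug is recorded. This may be a slip for Visit 2, but it bears on the same rule.

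6. **How large is the exposure?** At most 4 tablets × 200 mg = 800 mg of trial fluconazole per subject over four weeks. With the 30 planned subjects of Section 13.2, that is at most 30 × 4 = 120 tablets before any replacements, and fewer where the antifungal exception applies. The documents give no rate at which subjects start an interacting drug, so no case count can be given.

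**The case against.** The strongest reply is that the open rule is deliberate. Section 7 gives a reason for it, and being strict at entry but permissive for 28 days is a recognisable choice. The same pattern appears with steroids, which are excluded at entry while new immunomodulatory drugs are allowed later. Clinicians also keep general discretion. It stands that this is a low-priority alignment of texts and that no actual hazard has been shown. But the reason given does not explain why exclusion 8 exists, and discretion is a weak guide when the written rule says that there is no restriction.

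Three stronger readings are tempting.

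- A reader might infer that subjects are exposed to a known harmful interaction. The documents name no interacting drug and give no pharmacology at 200 mg weekly beyond Section 7's reassurance.
- A reader might infer that all subjects are at risk, or that fluconazole should be stopped in anyone who needs an interacting drug. Section 7 exempts those who continue their own systemic antifungal. That drug could itself be fluconazole, and the trial should not override it.
- A reader might see proof of an oversight in the handling of pregnancy. Section 7 says "Fluconazole is a pregnancy category D drug. As such, pregnant women will be excluded from this study", and Section 11.1 lists a positive test among possible reasons for stopping. But that list concerns study treatment, whereas the remedy here is to withhold the prophylaxis. The absence of interacting drugs from the list therefore shows little.

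**Conclusion.** The point holds as a low-priority, inexpensive safety improvement. The entry criterion and the on-study rule conflict for subjects who take trial-supplied fluconazole, and no other text in the documents closes the gap. It does not apply to subjects who remain on their own systemic antifungal.

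No harm rate, specific drug, or effect on power or alpha is claimed. The conclusion assumes that exclusion 8 was written for a reason that still applies after day 0. If the sponsor can show that Section 7's sentence is true for every drug, the remaining inconsistency is that exclusion 8 is not needed. The consent pages and the study manual were not available, so nothing is said about what they tell subjects or staff.

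**What to change.** - **Section 7 and synopsis:** replace the open rule with a statement that drugs with a strong fluconazole interaction should not be started while the subject takes trial-supplied fluconazole. If one becomes necessary, the trial-supplied fluconazole is withheld, but not an antifungal that the subject was already prescribed. Leave the separate restriction in Section 9.2 on therapies for the oral disease in place.
- **Section 7, sentence on drug levels:** qualify it to agree with exclusion 8.
- **Appendix 1:** add a line asking subjects to call the study team before they start a new drug.
- **Section 9.1.1:** name Visit 2 as a recording point, so that newly started drugs are captured.

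The sponsor and the investigational pharmacy should settle which drugs count.

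**Cost.** These are wording changes and one more recording point at an existing visit, with no new visit and no change to the analysis. The real downside is the loss of prophylaxis in the few subjects who need an interacting drug. Section 1.1.1 puts secondary candidiasis with topical steroids at 11–47%, and Section 7 warns that infection not detected early could confound the week 4 evaluation. The investigator should therefore consider other antifungal cover for those subjects.

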8 STUDY TREATMENTS

8.1 Method of Assigning Subjects to Treatment Groups

Randomization will be predetermined by a computer-generated list and coordinated by the UCSF Investigational Drugs Services Pharmacy. Patients will be assigned to one of two groups: 1) Arm A: compounded dexamethasone 0.5mg/5ml solution in Mucolox™ or 2) commercial dexamethasone 0.5mg/5ml solution only (ARM B).

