1 BACKGROUND

Oral Inflammatory Ulcerative Diseases are relatively common conditions seen in oral medicine practices. These include oral lichen planus (OLP), pemphigus vulgaris, mucous membrane pemphigoid (MMP) and oral chronic graft versus host disease (cGVHD).

Oral lichen planus

Oral lichen planus (OLP) is a benign, chronic condition that occurs in 1 to 2% of adults¹. Middle-aged women are twice as likely to be affected as men. OLP may be associated with a variety of systemic and local conditions and medication use such as thiazide diuretics, angiotensin converting enzyme (ACE) inhibitors, beta blockers, gold salts, sulfasalazine, sulfonyleureas and penicillamine. Biologic agents such as tumor necrosis factor (TNF) alpha inhibitors may also cause lichen planus-like eruptions². Amalgam and composite restorations may cause localized contact lichenoid hypersensitivity reactions possibly to mercury and formaldehyde.

OLP can affect any mucosal surface, and most commonly affects the buccal mucosa and tongue bilaterally. OLP can present with three distinct forms: reticular/keratotic, erosive/erythematous, and ulcerative forms. The reticular/keratotic form, characterized by Wickham striae, is the most common form and is often asymptomatic. Occasionally patients will report discomfort and describe the buccal mucosa as “rough,” “thick,” or “tight”. The erosive/erythematous form typically presents as desquamative gingivitis. Patients may complain of discomfort while eating acidic, spicy or crunchy food. The ulcerative form is the most severe and presents as shallow ulcerations that have a yellow fibrin membrane on the surface. Often, there is a combination of the three forms at different sites, or at different times. Most patients exhibit a characteristic bilateral and symmetric distribution of lesions, typically involving the buccal mucosa, dorsum and ventral surfaces of the tongue and/or gingiva.

The diagnosis of oral lichen planus is based primarily on clinical characteristics, although biopsy may be indicated when the presentation is not typical (e.g. unilateral presentation, or lack of reticulation features)^{3,4}. Histopathological examination demonstrates a lymphocytic band of variable thickness at the interface and degeneration or loss of the basal cell layer.

Mucous membrane pemphigoid

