2 STUDY RATIONALE

There is a significant unmet need for optimized topical therapies for Oral Inflammatory Ulcerative Diseases. Topical steroid therapy is considered the first line of treatment for Oral Inflammatory Ulcerative Diseases with current treatment regimens requiring multiple application or rinses daily^{27,32,33}. Although topical steroid therapy can be successful for most patients, the treatment schedule can be challenging to maintain. There is therefore considerable interest in developing new and more effective therapies that require less frequent applications. The possibility of having a treatment agent that is safe, easy to use, and cost effective, with potentially greater efficacy than the current standard of care available topical steroid solutions would be ideal. Using Mucolox™ as a vehicle to deliver topical dexamethasone to the oral mucosa has the potential to effectively prolong contact time between the medication and mucosa, leading to improved clinical outcomes due to the need for less frequent application. This technology would help to more efficiently achieve high drug concentrations locally. By possibly shortening the frequency and time of topical therapy and improving patient compliance, this may translate to greater therapeutic benefit. Our initial work in a small number of oral lichen planus patients has demonstrated the efficacy of dexamethasone 0.5mg/5mL solution in Mucolox™ in significantly improving signs and symptoms of OLP compared to dexamethasone 0.5mg/5mL solution only³¹. As such, dexamethasone 0.5mg/5mL solution in Mucolox™ has the potential to be used also for other Oral Inflammatory Ulcerative Diseases.

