9.2.1 Clinician Reported Outcomes

Mucosal disease will be measured using the REU scoring system for monitoring Oral Inflammatory Ulcerative Diseases³⁴. Assessment requires only a light source and a dental mirror. This is a validated semiquantitative instrument for monitoring reticular/hyperkeratotic, erosive/erythematous, and ulcerative OLP lesions. The oral cavity is divided into ten sites: right buccal mucosa, left buccal mucosa, tongue dorsum, tongue ventrum, maxillary gingiva, mandibular gingiva, floor of mouth, hard palatal mucosa, soft palate and tonsil, and labial mucosa (upper and lower together). The severity of each type of lesion is scored according to the presence or absence of reticulations/hyperkeratosis (0 = absent; 1 = present), and the size of the erosions/erythema or ulcers (in cm²) (0 = no involvement; 1-3 in increasing area of involvement). Because each type of lesion causes different degrees of discomfort and pain, each type of lesion is weighted accordingly: reticular lesions are weighted 1 because this presentation tends to be asymptomatic; erosive/erythematous lesions are weighted 1.5 since they tend to cause some degree of discomfort; ulcerative lesions are weighted 2.0 since they tend to be the most painful. The scores for each anatomic site are then totaled.

Intraoral photographs will be obtained at each visit.

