13.2 Sample Size, Accrual Rate and Study Duration

The sample size was calculated based on the data by Rhodus et al., as to ensure at least 80% power and two-sided alpha of 0.05 in detecting a t difference of 2.0 points oral pain on an 11 point scale (VAS 0-10) between Arm A and B²⁷. The mean expected change for Arm A will be 6.5 points reduction with a standard deviation of 1.4 points. The mean expected change for Arm B will be 4.5 points reduction with a standard deviation of 1.4 points.

A total of 15 patients per arm will be enrolled (total of 30 subjects). The proposed sample size includes a loss of follow up of 5%. Approximately 60 patients per year are diagnosed with Oral Inflammatory Ulcerative Diseases at the Sol Silverman Oral Medicine Clinic at UCSF. We anticipate the accrual rate will be approximately 2 patients per month, thus the accrual goal will be achieved in approximately 15 months.

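### VAS and REU change are compared between arms with no diagnosis term, although at least four diseases are pooled in 30 patients

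*Combined protocol and SAP*

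**What the plan says.** Section 1 defines the study population as a family of diseases: "These include oral lichen planus (OLP), pemphigus vulgaris, mucous membrane pemphigoid (MMP) and oral chronic graft versus host disease (cGVHD". Section 6.2 admits "Patients with symptomatic (worst VAS sensitivity score ≥ 7 over the last week) Oral Inflammatory Ulcerative Diseases" and sets no quota or cap per disease. Section 13.2 gives the size: "A total of 15 patients per arm will be enrolled (total of 30 subjects".

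The main text on allocation is in Section 8.1: "Randomization will be predetermined by a computer-generated list and coordinated by the UCSF Investigational Drugs Services Pharmacy". It names two arms but gives no strata, blocks or ratio. Section 13.1.1 compares VAS change between arms by t-test or Mann-Whitney test, and Section 13.1.2 does the same for REU. Neither includes a diagnosis factor or a table by diagnosis. Section 13 also says that a detailed SAP, which may modify these analyses, is still to be written.

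The planning figures and earlier experience come from OLP. Section 13.2 bases its assumptions on a study that Section 1.1.2 describes as 13 patients with erosive-ulcerative OLP. The previous Mucolox study (Section 1.1.3) was also in OLP. From that work, Section 2 infers that the product "has the potential to be used also for other Oral Inflammatory Ulcerative Diseases". Section 9.2.1 says of REU: "This is a validated semiquantitative instrument for monitoring reticular/hyperkeratotic, erosive/erythematous, and ulcerative OLP lesions".

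**The concern.** The protocol's background describes two kinds of disease. OLP and oral cGVHD are lichenoid and share similar topical therapy. Pemphigus vulgaris (PV) and MMP are autoantibody blistering diseases, whose severe or refractory cases may need systemic agents. REU has a reticulation component, which the background describes for OLP and cGVHD but not for PV or MMP. It is therefore plausible, though not shown, that VAS and REU change differ by diagnosis.

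If they do, two things follow in a trial of 15 per arm. The spread between diagnoses enters the error term and costs power. A draw that puts several more blistering cases in one arm also moves the observed difference, and the planned analysis would neither correct this nor show it. In addition, a sample made up mostly of OLP could be reported under the broad disease label without the reader seeing the mix.

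**Working it through.** **The plan's own size.** Inputs from Section 13.2: reductions of 6.5 and 4.5 points (difference 2.0), SD 1.4 in each arm, two-sided alpha 0.05, 80% power, 5% loss.
- Normal approximation: n = 2 × (1.960 + 0.842)² × 1.4² / 2.0² = 7.7, so 8 per arm, or 9 after dividing by 0.95.
- Exact t-test: 8.76, so 9 per arm, or 10 after 5% loss.
- The stated 15 per arm is not reproduced. It gives 96.5% power (95.3% with 14), so the plan has a reserve above 80%.

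**Chance imbalance.** Assumption: K of the 30 patients have blistering disease, split at random 15/15. The documents give no case mix. The probability that a of them fall in Arm A is C(K,a) × C(30−K,15−a) / C(30,15), and the gap between arms is |2a − K|.

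| K | P(gap ≥ 4) |
|---|---|
| 3 or fewer | 0 |
| 4 | 10.0% |
| 5 | 4.2% |
| 6 | 16.9% |
| 8 | 21.5% |
| 10 | 24.5% |

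These figures count both directions. The chance of a gap against one named arm is half as large: about 8%, 11% and 12% for K = 6, 8 and 10.

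**Shift from a gap of 4.** With 15 per arm, the shift is (4/15) × d = 0.27 × d. Here d is the difference in mean VAS improvement between disease groups (assumed).
- d = 1: 0.27 points, 13% of the 2.0-point target
- d = 2: 0.53 points, 27%
- d = 3: 0.80 points, 40%

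**Precision of the unadjusted test.** Take 1.4 as the SD within a disease group, a further assumption prompted by its origin in an OLP-only study. The SD over the mix is then √(1.4² + p(1−p)d²), with p = K/30. Power for 2.0 points with 15 per arm:

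| d | K = 6 | K = 10 |
|---|---|---|
| 1 | 95.3% | 94.7% |
| 2 | 90.6% | 87.9% |
| 3 | 81.8% | 75.7% |

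**What adjustment and stratification recover.** Simulation with K = 10, SD 1.4 and 10,000 runs per scenario:

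| d | Unadjusted, unstratified | Adjusted only | Adjusted and stratified |
|---|---|---|---|
| 0 | 96.6% | 95.8% | 96.5% |
| 2 | 87.8% | 95.9% | 96.3% |
| 3 | 74.9% | 95.7% | 96.9% |

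Type I error of the unadjusted, unstratified test was 4.9%, 4.9% and 5.3% for d = 0, 2 and 3.

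**Results within one disease.** An even split over four diseases gives 30/4 = 7.5 patients each, so 3 to 4 per arm. Power for 2.0 points is then 27% to 40%, and the 95% interval has a half-width of 3.2 to 2.4 points. Results by diagnosis can only be descriptive.

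**The case against.** The strongest reply is that randomisation already protects the comparison, and the simulation agrees. A reader might infer that pooling biases the trial or invalidates the test. It does neither: the distortion exists only given an unlucky draw and a real prognostic difference.

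The documents do not establish that difference. Section 1 calls topical corticosteroids or tacrolimus the mainstay for PV and lists topical corticosteroids among the treatments for MMP. Section 1.1.1 calls topical corticosteroids the mainstay for the whole group. Section 9.2.3 calls oral cGVHD very similar to the other diseases. Systemic agents are mentioned for severe or refractory cases, and patients already on steroids are excluded. The values of d and K are therefore assumptions. Section 1 calls PV uncommon, so K may be small. At d = 2 the unadjusted power stays well above the planned 80%.

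A reader might also infer that the trial cannot support its claim for diseases other than OLP. The objective in Section 3.1 is one pooled comparison, and Section 2 speaks only of potential use in the others. No separate claim is made for PV, MMP or cGVHD, and a pooled effect for the enrolled mix can be estimated. Similarly, Section 9.2.1 presents REU for monitoring the whole disease group as well as for OLP lesions, so the text does not show that it is unsuitable outside OLP.

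Finally, that the list is unstratified is read from silence. The list may have strata that the protocol does not mention, and the later SAP could add adjustment.

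All of this stands. It leaves intact that the analysis as written has no diagnosis term and no reporting by diagnosis, and that adding both costs very little.

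**Conclusion.** The point holds as an inexpensive improvement in precision and interpretability. It is not a flaw that invalidates the trial. No stratification is stated and no adjustment for diagnosis is planned. With 10 of 30 blistering cases and a 2-point prognostic difference, adjustment raises power from about 88% to 96%; with 3 points, from about 75% to 96%. If diagnosis is not prognostic, it costs about one point of power or less. The gains rest on an assumed case mix, an assumed d, and 1.4 being the SD within disease groups. They shrink towards nothing as K or d becomes small.

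Stratifying the list adds 0.4 to 1.2 points of power beyond adjustment in these two scenarios (96.3 − 95.9 and 96.9 − 95.7). It would not create evidence for individual diseases, because the obstacle there is the number of patients. That part is met by showing the mix and wording the conclusions to match.

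**What to change.** - **Sections 13.1.1 and 13.1.2, or the SAP before final data are analysed:** compare VAS and REU change with a linear model containing arm and a two-level diagnosis factor: lichenoid (OLP, oral cGVHD) and blistering (PV, MMP). Give a rule for any other eligible diagnosis, since the list in Section 1 is not closed. Four levels would be too thin for 30 patients.
- **Visit 1 form (Appendix 3):** add an explicit diagnosis field. Section 9.1.3 already collects history of the current disease, but the form as reproduced shows no such field.
- **Diagnostic definition:** the synopsis requires biopsy-proven disease, while Section 6.1 relies on clinical diagnosis and Section 6.2 mentions no biopsy. These must be reconciled so that the factor has one definition.
- **Reporting:** tabulate VAS and REU results by arm and diagnosis descriptively, and limit conclusions to the diagnoses actually enrolled.
- **Section 8.1:** state whether the list has strata or blocks. Two strata at the pharmacy are optional. Small blocks in an open-label trial make the next allocation easier to guess, and the blistering stratum may end with an incomplete block.

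The cost is one form field, a few lines of text and one degree of freedom. No extra patients or visits are needed.
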